### **8.1.2. Early Termination Visit**

Subjects who are withdrawn from the study treatment before the primary endpoint visit (week 17) will be asked to return to the study site once for an early termination visit consisting of the end of treatment assessments described in [Table 3](#), which includes an end of treatment NAC. Subjects should return as soon as possible for the end of treatment assessment, so that the NAC assessment may be performed while study drug(s) (dupilumab or placebo for dupilumab and SCIT or placebo for SCIT) were recently administered. Subjects who are withdrawn from the study treatment after the primary endpoint visit will be asked to return to the study site for early termination assessments, including NAC.

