#### 5.4. Post-Treatment Follow-up Period (8 Weeks):

All subjects who complete or prematurely discontinue the treatment will be assessed for safety, laboratory, and clinical assessments as noted in the Schedule of Events (Table 3) 8 weeks after the end-of-treatment.

The duration of the 8-week follow-up period is based on the time expected for drug concentrations to approach the lower limit of quantification after the last dose of dupilumab.

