### 7.3.2. Study Drug Discontinuation (Dupilumab or Placebo for Dupilumab and SCIT or Placebo for SCIT)

If one study drug (dupilumab or placebo for dupilumab and SCIT or placebo for SCIT) is discontinued, all study drugs (dupilumab or placebo for dupilumab and SCIT or placebo for SCIT) must be discontinued.

Subjects who permanently discontinue from study drug (dupilumab or placebo for dupilumab and SCIT or placebo for SCIT) and who do not withdraw from the study will be asked to return to the study site within 2 weeks of stopping study drug (dupilumab or placebo for dupilumab and SCIT or placebo for SCIT), if possible, to undergo their end of treatment visit, including NAC. Anti-histamines may not be taken within 5 days of NAC.

Subjects who permanently discontinue from study drug (dupilumab or placebo for dupilumab and SCIT or placebo for SCIT) and who opt to withdraw from the study will be asked to complete study assessments as per end of treatment visit immediately, within 2 weeks of stopping study drug (dupilumab or placebo for dupilumab and SCIT or placebo for SCIT), if possible, including NAC, per Section 8.1.2.

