**Table 3: Schedule of Events**

Study Procedure	Screening Period				Treatment Period												EOT NAC V16	V17	Unscheduled Visit (if applicable) 	EOS V18	ET
	V1	V2	NAC V3	R  V4	V5	V6	V7	V8	V9	V10	V11	V12	V13	V14	V15						
Week (W)					1	2	3	4	5	6	7	8	10	13	16	17	20		24		
Study Day	+1 to -84				1	8	15	22	29	36	43	50	57	71	92	113	120	141		169	
Window in Weeks	±1				-1	±1	±1	±1	±1	±1	±1	±1	±1	±1	±1	±1	±1	±1		±3 	
Screening/Baseline																					
Inclusion/Exclusion	X	X	X	X																	
Informed Consent	X																				
██████████	X																				
██████████																					
██████████																					
Medical History	X																				
Demographics	X																				
Randomization (R)				X																	
SPT for Timothy Grass	X																				
Serum Timothy Grass sIgE	X																				
Treatment:																					
Dupilumab/PBO loading 				X																	
Dupilumab 300 mg q 2 weeks dosing 					X	←-----X-----→												X			
Visit for SCIT Injections 					X	X 	X	X 	X	X 	X	X	X 	X	X 			X			
Premedicate with loratadine 10 mg orally 					X	X	X	X	X	X	X	X	X	X	X			X			
Training for Self-injection (dupilumab/PBO)				X																	
Dupilumab/PBO distribution				X		X						X		X				X			

Study Procedure	Screening Period			Treatment Period												EOT NAC V16	V17	Unscheduled Visit (if applicable) 	EOS V18	ET
	V1	V2	NAC V3	R  V4	V5	V6	V7	V8	V9	V10	V11	V12	V13	V14	V15					
Week (W)					1	2	3	4	5	6	7	8	10	13	16	17	20		24	
Study Day	+1 to -84			1	8	15	22	29	36	43	50	57	71	92	113	120	141		169	
Window in Weeks	±1				-1	±1	±1	±1	±1	±1	±1	±1	±1	±1	±1	±1	±1		±3 	
Dupilumab/PBO diary review/ Accountability 						←-----X-----→												X		X
Subject Dosing Diary 				X		X		X		X		X	X	X				X		X
Concomitant Meds	X	X	X	X	X	X	X	X	X	X	X	X	X	X	X	X	X	X	X	X
Efficacy:																				
TNSS		X	X											X		X				X
TOSS			X													X				X
PNIF			X													X				X
Intradermal skin challenge testing (LPR)			X													X				X
Skin Prick Test with Serial Allergen Titration (EPR)			X													X				X
Safety:																				
Weight	X		X													X		X		X
Height	X																			
Vital Signs	X		X	X	X	X	X	X	X	X	X	X	X	X	X	X	X	X	X	X

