#### 9.4.3. Other Events that Require Accelerated Reporting to Sponsor

The following events also require reporting to the sponsor (or designee) within 24 hours of learning of the event:

**Symptomatic Overdose of Study Drug:** Accidental or intentional overdose of at least 2 times the intended dose of study drugs within the intended therapeutic window, if associated with an AE,

**Pregnancy:** Although pregnancy is not considered an AE, it is the responsibility of the investigator to report to the sponsor (or designee), within 24 hours of identification, any pregnancy occurring in a female study subject during the study or within 12 weeks of the last dose of study drugs. Any complication of pregnancy affecting a female study subject and/or fetus and/or newborn that meets the SAE criteria must be reported as an SAE. Outcome for all pregnancies should be reported to the sponsor.

**Adverse Events of Special Interest (AESIs):** All AESI, serious and nonserious, must be reported within 24 hours of identification using the same reporting process as for SAE reporting, per Section 9.4.2. Adverse events of special interest for this study include the following: anaphylactic reactions, systemic or severe hypersensitivity reactions, malignancy (except in-situ carcinoma of the cervix, non-metastatic squamous or basal cell carcinoma of the skin), helminthic infections, suicide-related events, any type of conjunctivitis or blepharitis (severe or serious or lasting  $\geq 4$  weeks), keratitis.

Refer to the study manual for the procedures to be followed.

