#### **9.4.6. Follow-up**

Adverse event information will be collected until the subject's last study visit.

Serious adverse event information will be collected until the event is considered chronic and/or stable.

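### Scheduled safety visits and routine adverse-event collection can end before the protocol's own 8-week post-treatment period, because its sections conflict

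*Protocol*

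**What the plan says.** **Follow-up of subjects who stop treatment early**

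- Protocol 5.4: "All subjects who complete or prematurely discontinue the treatment will be assessed for safety, laboratory, and clinical assessments", 8 weeks after end of treatment. The reason given is pharmacokinetic, with the time counted from the final dupilumab injection: "The duration of the 8-week follow-up period is based on the time expected for drug concentrations to approach the lower limit of quantification". SAP 2.3 repeats that premature discontinuers are assessed under the schedule of events, but without the 8 weeks.
- Protocol 8.1.2: subjects withdrawn from treatment before week 17 "will be asked to return to the study site once for an early termination visit". Protocol 6.3 sends subjects withdrawn from treatment to this section.
- Protocol 7.3.2 separates two groups. Those who stop drug but stay in the study "will be asked to return to the study site within 2 weeks of stopping study drug", if possible. Those who also leave the study "will be asked to complete study assessments as per end of treatment visit immediately, within 2 weeks of stopping study drug", if possible. No later visit is named for either group.
- Protocol 9.4.6: "Adverse event information will be collected until" the subject's last study visit.

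**End-of-study visit (V18)**

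- Table 3 puts V18 at week 24, day 169, with an entry of ±3 in the row headed "Window in Weeks". Footnote 18, attached to that entry, asks for the visit to be close to the scheduled date and the window to be used only when needed, but it refers to days. SAP 10.2 carries over both the row and the footnote.

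**Analysis**

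- TEAE incidence through end of study is a secondary endpoint (Protocol 4.2.2).
- SAP 3.3 ends the treatment period at last dose plus 14 days when there is no week 17 visit. It limits follow-up-period summaries to subjects with at least one visit after the week 17 NAC.
- SAP 6.3 maps ET and EOS visits by study day: days 131 to 155 are Week 20, and Week 24 starts at day 156.

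**The concern.** The sponsor chose 8 weeks so that safety observation lasts until dupilumab is nearly cleared. Two parts of the protocol let observation end sooner.

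The first affects subjects who stop early. Some of them stop for the reasons listed in Protocol 7.3.3: an anaphylactic reaction, certain infections, or severe laboratory abnormalities. A site that reads 8.1.2 as complete can hold one visit and close the subject, although 5.4 expects an assessment 8 weeks after treatment. Table 3 encourages that reading, because apart from screening the serum pregnancy test is scheduled only at EOS and ET, as if ET were a final visit.

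The second affects completers whose final visit is held at the early edge of its window.

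In the overall TEAE summary, a subject seen only at ET stays in the safety-set denominator and counts as event-free for the unobserved days. If early stopping differs between arms, TEAE proportions are compared over unequal observation. Laboratory values near the end of washout would also be missing for these subjects.

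**Working it through.** **Inputs.** Last scheduled dose: week 16, day 113 (Protocol Tables 2 and 3). Dupilumab dosing window: ±3 days (footnote 3), read here as days 110 to 116. V18: day 169, ±3 (Table 3). Early termination visit: within 14 days of stopping, if possible (7.3.2). Planned arm size: 25.

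**Step 1. Reproduce the stated 8 weeks.** 169 − 113 = 56 days = 8.0 weeks. The figure matches when counted from the last dose. From the week 17 NAC (day 120) it would be 169 − 120 = 49 days, or 7 weeks.

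**Step 2. Early stoppers seen once.** Unobserved days = 56 − (days from last dose to the ET visit).

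- ET visit 14 days after the last dose: 56 − 14 = 42 days, and 42/56 = 75%.
- If the decision to stop comes a full dupilumab interval (14 days) after the last dose and the visit 14 days after that: 56 − 28 = 28 days, or 50%. This timing is an assumption, used to show the range.
- An ET visit sooner than 14 days after the last dose leaves more than 42 days unobserved.

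Where the only visit falls within 14 days of the last dose, all of the subject's observation lies in the SAP treatment period. The subject has no later visit and so leaves the follow-up-period summary.

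**Step 3. Effect per arm.** Planned post-dose follow-up is 25 × 56 = 1,400 subject-days. Each such subject loses 42, and 42/1,400 = 3%. The documents give no early-stopping rate. If 1, 3 or 5 of 25 were affected (assumed), the loss would be 3%, 9% or 15% of the arm's post-dose follow-up.

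**Step 4. V18 window.**

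| Reading of ±3 | Earliest V18 | Days after day-113 dose |
|---|---|---|
| Weeks (row label) | 169 − 21 = day 148 | 148 − 113 = 35 (5.0 weeks) |
| Days (footnote 18) | 169 − 3 = day 166 | 166 − 113 = 53 (7.6 weeks) |

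With the dupilumab dosing window, the weeks reading gives 148 − 116 = 32 to 148 − 110 = 38 days. Against 56 days, 35 is shorter by 21/56 = 37.5%.

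**Step 5. SAP mapping.** An EOS visit on days 148 to 155 falls in the Week 20 window (131 to 155). V17 (day 141, ±1 week) can also reach 141 + 7 = day 148, so the two visit windows meet. SAP 6.3 prefers the scheduled visit within a window. A subject who had V17 could therefore have early EOS values passed over at Week 20 and none at Week 24. SAP 6.3 also says that scheduled visits are not windowed, and V18 is both scheduled and the EOS visit, so which rule governs is itself unclear. Read as days, the earliest V18 (day 166) falls in Week 24 and the problem does not arise.

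**The case against.** The strongest reply is that 5.4 already settles the matter. It names premature discontinuers expressly, and 8.1.2 can be read as describing one visit type, the ET visit with its NAC, without cancelling the later assessment. That is fair as a reading of intent. It does not remove the conflict for a site: 6.3 points to 8.1.2, and neither 8.1.2 nor 7.3.2 refers back to 5.4 or V18.

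A reader might infer several stronger things that the documents do not support.

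- *That follow-up of early stoppers is 2 weeks by rule.* It is not. Section 5.4 requires more, the 2 weeks is qualified by feasibility, and a subject who withdraws from the study altogether cannot be held to later visits.
- *That serious events and pregnancies go uncollected.* Protocol 9.4.2 covers SAEs the investigator learns of with onset within 30 days of end of study, or of the last dose after early termination, and fatal or drug-related SAEs after that. Protocol 9.4.3 covers "any pregnancy occurring in a female study subject during the study or within 12 weeks of the last dose of study drugs". Abnormal laboratory results must be repeated (8.2.2.6), and unscheduled visits are available (8.1.3). What is exposed is scheduled testing and routine capture of non-serious events.
- *That 12 weeks is a drug-exposure period which visits should span.* Only the 8 weeks is tied to drug concentration. The 12 weeks governs contraception and pregnancy reporting, and no section promises a visit at that point.
- *That all early stoppers stopped for safety.* Protocol 6.3 allows withdrawal from the study for any reason.

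On the window, footnote 18 limits its use, and its mention of days may be loose wording. That reduces how often the 5-week case would occur, but does not settle the unit. SAP 5.6.2 tabulates observation time, so unequal follow-up would be visible, though the TEAE proportions are not adjusted for it.

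**Conclusion.** The point holds as an inconsistency to be resolved. It does not show that the protocol sets too short a follow-up. Where 8.1.2 is followed alone, about 42 of the 56 days in 5.4 lack scheduled visits and routine non-serious AE collection, and the subject leaves the SAP follow-up summary. This assumes the ET visit falls 14 days after the last dose. The number of subjects affected is unknown.

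For completers, the earliest permitted final visit is 35 days after the last dose if the window is in weeks, as labelled, and 53 if it is in days. Both assume a day-113 dose and are short of 56, but only the weeks reading conflicts with the SAP Week 24 window. The matter should be corrected because it concerns safety data and the sponsor's own stated basis for follow-up.

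**What to change.** 1. Reconcile Protocol 8.1.2 and 7.3.2 with 5.4, so that subjects who stop treatment but stay in the study have the ET visit and also the V18 safety assessments that 5.4 already states. Add the cross-reference in 8.1.2, and carry the 8 weeks into SAP 2.3.
2. State the unit of the V18 window in Table 3 and footnote 18, and in SAP 10.2.
3. Reconcile the early edge of that window with the 8-week basis in 5.4, counted from the actual last dose. Removing the early side around day 169 would not be enough: after a dupilumab dose on day 116, day 169 is only 169 − 116 = 53 days later.
4. Reconcile the same edge with the SAP 6.3 Week 24 window, and say whether V18 is mapped by study day or kept as a scheduled visit.

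The cost is protocol and SAP wording, one further safety visit for each early stopper who stays in the study, and some slightly later EOS visits. Pregnancy reporting needs no change on this account.

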### 3.2.6. Rationale for Nasal Allergen Challenge

This study will use the NAC to assess the efficacy of dupilumab with or without SCIT on allergic symptoms outside of grass allergy season. The NAC is a well-recognized nasal provocation model that reproduces direct allergen contact of the upper airways in a controlled clinical setting allowing for rapid proof-of-mechanism (POM) in smaller numbers of patients than natural exposure studies (Eckman, 2010) (Paterniti, 2011). Intranasal instillation of allergen causes local allergic symptoms, such as nasal congestion, itching, sneezing and rhinorrhea, which peak within the first hour of the early phase reaction (EPR) (Scadding, 2015a). Within minutes of local allergen exposure, IgE-mediated basophil and tissue mast cell degranulation occurs with the release of mediators, which cause blood vessel dilation and vascular leakage immediately leading to these nasal symptoms. Therefore, the change in TNSS score after NAC with Timothy Grass extract is selected for POM as a reliable, reproducible, and controlled method of measuring allergy symptoms for this study. Each subject will undergo a baseline NAC at screening and a repeat NAC at the end of treatment.

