## 5.2. Screening

After obtaining informed consent, subjects will be assessed for eligibility during a 3-part screening period. The 3-part screening period is up to 12 weeks. As this is an off-season study that must begin and end outside of grass season, sufficient screening time is necessary so that subjects may be enrolled efficiently. During screening visit 1, subjects with a history of allergic rhinitis to grass pollen will undergo a medical history, physical examination, SPT for Timothy Grass, and blood draw for Timothy Grass specific IgE. If the subject meets criteria with a positive SPT for Timothy Grass and for Timothy Grass specific IgE as per Inclusion/Exclusion criteria, they will be invited for screening visit 2. At screening visit 2 they will undergo a pregnancy test if applicable, spirometry, electrocardiogram (ECG), serologic testing for chronic viral infections (Human Immunodeficiency Virus Infection [HIV] and Hepatitis B and C), hematology, chemistry, urinalysis, will be evaluated for the study eligibility criteria, and will undergo a baseline nasal brushing. The baseline nasal brushing must occur while  $TNSS \leq 2$  and it must be at least 28 days prior to the screening visit 3/Entry visit, so that the nasal mucosa may re-epithelialize and return to a resting state prior to NAC. If the subject reports nasal symptoms and has a  $TNSS > 2$  at Screening visit 2, they can be rescheduled for screening visit 2 when they

are no longer symptomatic- for re-evaluation by TNSS. The baseline nasal brushing should not be performed if the 28 day waiting period until the NAC will compromise the subject's ability to complete the 16 week treatment period and final week 17 NAC prior to the subsequent allergy season (eg, subjects cannot have any expected seasonal or environmental allergic symptoms at the week 17 NAC visit). If however, the full 16 week treatment period and week 17 NAC visit is expected to be completed prior to the subsequent allergy season, subjects should undergo baseline nasal brushing. Forgoing the baseline nasal brushing in this case will not be considered a protocol deviation, but the event will be recorded and justified. It is expected that subjects who are enrolled in the final month of the enrollment period, as described in the Study Operations Manual, will not undergo the baseline nasal brushing.

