#### 5.6. Planned Interim Analysis

No interim analysis is planned. An unblinded first-step analysis may be performed once all subjects in the study have completed the 16-week treatment period and performed NAC at week 17 as specified in the protocol (visit 16 or earlier for those subjects who are withdrawn prematurely from the study). If performed, this first-step analysis will be considered the final analysis for the primary endpoint and secondary efficacy endpoints up to end of treatment NAC visit 16 (week 17). A description of the statistical methods to be employed and blinding implications are in Section 10.4.3.4.

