#### 8.2.1.5. Nasal Fluid Collection

Nasal fluid is collected during the 2 NAC study visits to determine the levels of cytokines and chemokines produced in response to NAC. Nasal fluid is collected (1) at the initial NAC visit: at baseline prior to NAC and over the course of 6 hours after NAC and (2) at the 17 week (on study drug) NAC visit at baseline prior to NAC and over the course of 6 hours after NAC.

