## 4.5. Efficacy Variables

### 4.5.1. Primary Efficacy Variable (s)

The primary endpoint in the study is:

- Percent change in AUC for TNSS (0-1 hr post peak TNSS) in response to a NAC at week 17 from the pretreatment baseline TNSS AUC (0-1 hr post peak TNSS) for dupilumab + SCIT as compared to SCIT

The algorithm for calculating the area under curve (AUC) is provided in Section [6.2](#).

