#### Total Nasal Symptom Score (TNSS)

The Total Nasal Symptom Score (measured on a 0 to 12 scale) is a patient-reported composite symptom assessment of 4 symptoms graded on a 0 (none) to 3 (severe) scale: rhinorrhea, nasal congestion, nasal itching, and sneezing. The TNSS will be performed at Screening Visit 2 and each NAC visit (Screening Visit 3 and Visit 16). At the end of treatment (EOT) NAC (week 17), subjects will be observed for approximately 10 minutes and a resting/baseline TNSS  $\leq 2$  must be achieved, signifying that the subject does not have active nasal symptoms at rest (due to viral infection, sinusitis, allergies, etc.), prior to NAC. The NAC will be performed using increasing doses of Timothy Grass extract every 10 minutes, with TNSS score recorded approximately every 10 minutes (up-titration symptom score), up until they reach the concentration of Timothy Grass extract that was used to achieve a Total Nasal Symptom Score (TNSS)  $\geq 7$  at their baseline NAC visit. This TNSS score will be recorded. After recording the TNSS attained using concentration of Timothy Grass extract that was used to achieve a Total Nasal Symptom Score (TNSS)  $\geq 7$  at their baseline NAC visit, the subject will be observed for the subsequent hour and the TNSS will be recorded at 5 minutes, 15 minutes, 30 minutes, 45 minutes, 1 hour, and then hourly up to 6 hours.

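### Early leavers who already have a valid week-17 challenge are still asked for another NAC, which fits neither the two-challenge design nor any planned endpoint

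*Protocol*

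**What the plan says.** Protocol 8.1.2 has two branches. Subjects withdrawn from treatment before week 17 come back once for the end-of-treatment assessments with NAC: "Subjects should return as soon as possible for the end of treatment assessment". The reason given is that the challenge should take place while drug was recently given. Those withdrawn from treatment later "after the primary endpoint visit will be asked to return to the study site for early termination assessments, including NAC".

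Table 3 has one ET column for both branches. It marks TNSS, TOSS, PNIF, the intradermal test, the titrated skin prick test, nasal brushing and nasal fluid. The follow-up visits V17 (week 20) and V18 (week 24) carry none of these.

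Other sections provide for two challenges:

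- Protocol 3.2.6: "Each subject will undergo a baseline NAC at screening and a repeat NAC at the end of treatment".
- Protocol 8.2.1.5: "Nasal fluid is collected during the 2 NAC study visits".
- SAP 4.5.1 places the TNSS at Screening Visit 2 and at "each NAC visit (Screening Visit 3 and Visit 16".

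Protocol 7.3.2 asks subjects who stop study drug permanently to have the end-of-treatment visit, with NAC, no later than two weeks after stopping, if possible.

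**The concern.** Tables 1 and 2 of the protocol place the last SCIT and dupilumab doses in week 16. After the week-17 visit there is no planned dose left to be withdrawn from. The second branch of 8.1.2 therefore either does nothing or is applied to people who leave during follow-up, most of whom would already have had their endpoint challenge.

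A site that applies it that way would ask a leaving subject for another escalating allergen challenge with assessments to 6 hours, prick and intradermal allergen, and another brushing. Subjects who complete follow-up are asked for none of this. Protocol 9.4.1 keeps expected NAC symptoms out of adverse-event reporting because they are recorded as outcomes. Here they would be outcomes of a challenge that no planned endpoint uses.

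At stake are subject burden and clear instructions to sites. The primary comparison is not.

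**Working it through.** The plan gives no figure for this point. Its sample size and power do not depend on a challenge after week 17. The check compares passages and counts study days.

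**Inputs.** Last planned dose: day 113 (week 16). Week-17 NAC (V16): day 120. End of study (V18): day 169. All three are from Table 3. SAP 6.3 windows for ET visits: week 17 = days 117–130, week 20 = days 131–155, week 24 = day 156 onward.

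**Step 1: who is covered.** Dupilumab is planned every 14 days from day 1 to day 113 (1 + 8 × 14 = 113), and the last SCIT visit is also day 113. No planned dose falls after day 120. Read literally, the second branch of 8.1.2 has no members.

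**Step 2: when the challenge would fall if applied to follow-up leavers.**

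| ET NAC on day | Days since V16 | Days since last dose | SAP 6.3 visit | Use for a NAC endpoint |
|---|---|---|---|---|
| 121–130 | 1–10 | 8–17 | Week 17 | Only if the scheduled week-17 value is missing |
| 131–155 | 11–35 | 18–42 | Week 20 | None defined |
| 156–169 | 36–49 | 43–56 | Week 24 | None defined |

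**Step 3: fit with the protocol's own timing.** The two-week limit in 7.3.2, counted from day 113, ends on day 113 + 14 = 127. The scheduled NAC comes 120 − 113 = 7 days after the last dose. A challenge on day 169 would come 169 − 113 = 56 days (8 weeks) after it, which does not match the stated reason of recent dosing.

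**Step 4: endpoints.** The primary variable is "Percent change in AUC for TNSS (0-1 hr post peak TNSS) in response to a NAC at week 17". Every secondary and exploratory NAC endpoint is also set at week 17 (Protocol 4.2; SAP 4.5). SAP 6.3 takes the scheduled visit first and turns to an ET value only when there is none. The LOCF sensitivity analysis (SAP 5.7.1) imputes week 17, so it does not need a later value. If the first-step analysis is done, Protocol 5.6 makes it the "final analysis for the primary endpoint and secondary efficacy endpoints up to end of treatment NAC visit 16".

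**Step 5: brushing interval.** Protocol 5.2 and 8.2.1.4 require at least 28 days between the baseline brushing and the screening NAC, for mucosal recovery. Table 3 footnote 16 gives the same minimum between the on-drug brushing and the final NAC. V16 itself ends with a brushing 6 hours after challenge. Day 120 + 28 = day 148, so a repeat NAC on days 121–147 falls inside 28 days. That is 27 of the 49 days from 121 to 169. At week 20 the gap is 141 − 120 = 21 days.

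These counts take V16 on its target day. If V16 moves within its window, the day-148 limit moves with it; the SAP windows do not.

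**The case against.** The strongest reply is that the text does not order a third challenge at all. Section 8.1.2 speaks of withdrawal from treatment, the protocol elsewhere separates that from leaving the study, and 7.3.2 ties the discontinuation NAC to two weeks after stopping drug. Read together, these call for nothing at week 20 or 24. A reader might infer that the plan mandates a third challenge for everyone who leaves follow-up. The documents do not say so. What remains is a sentence with no members as worded, next to an ET column that makes no distinction, and a site could well apply both.

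A reader might also infer that such a challenge could never yield useful data. That goes too far. V16 can fail its preconditions (resting TNSS, antihistamine washout, peak flow in subjects with asthma), and an ET NAC on days 121–130 could then supply week 17. SAP 6.3 also leaves later ET values open to by-visit summary. The nasal samples go to a separate exploratory biomarker report whose plan is not in these documents. None of this gives a purpose for repeating a valid week-17 challenge.

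A third inference is that the challenge would fall in grass season. The subject-level check in 5.2 asks only whether the subject can "complete the 16 week treatment period and final week 17 NAC prior to the subsequent allergy season", and the Introduction calls it a 17-week off-season study. But the Synopsis puts the entire study off-season, 5.2 says it must begin and end off-season, and no season dates are given. The question cannot be settled from the documents.

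Finally, the two-challenge passages describe the schedule, and an early-termination rule may depart from it. It may, but then its purpose and analysis should be stated, and they are not.

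**Conclusion.** The point holds in limited form. For a subject with a valid week-17 NAC, the ET repeat does not fit the two-challenge sections, the 7.3.2 limit or the reason in 8.1.2, and it serves no planned NAC endpoint. Before day 148 it also falls inside the 28-day interval the protocol sets elsewhere between a brushing and a challenge. The exception is a subject without a valid week-17 value whose ET NAC falls on days 121–130.

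This rests on reading the second branch of 8.1.2 as aimed at follow-up leavers, the only reading that gives it effect on the planned schedule. The documents give no rate of leaving after week 17, so the number affected is unknown. Purely as an illustration, 2% to 10% of about 100 subjects would be 2 to 10 people asked, and some may decline. The planned efficacy comparisons and the power are unaffected. It is worth correcting because the burden is avoidable and the change is small.

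**What to change.** Reconcile Protocol 3.2.6, 7.3.2, 8.1.2 and 8.2.1.5, the ET column of Table 3, and the copy of that table in SAP 10.2:

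1. Make the ET NAC and its linked assessments (TNSS, TOSS, PNIF, intradermal and prick tests, brushing, nasal fluid) conditional on the subject not yet having a valid end-of-treatment NAC, and say what counts as valid.
2. Give subjects who already have one the V18 assessments. These keep adverse events, laboratory tests, ECG, PK and ADA.
3. Replace the trigger in the last sentence of 8.1.2 so that it names the people it is meant for.
4. If the sponsor does want a NAC after week 17, state its purpose and analysis. This includes how one after day 130 would be handled in a subject with no valid week-17 value, since SAP 6.3 would not assign it to week 17.

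Sending everyone who leaves after V16 to the V18 assessments would be simpler. It would, however, lose a usable NAC from a subject who attended V16 without a valid challenge.

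The cost is one sentence and one table footnote, repeated in the SAP table. The only data given up are off-schedule exploratory nasal samples that no described analysis uses.
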